### 9.3.3 Efficacy Analyses

#### 9.3.3.1 Vehicle-Controlled Treatment Period

The comparison between the groups for the exploratory efficacy endpoints will be done using a mixed model repeated measures (MMRM), where the change from baseline will be the dependent variable; the treatment group, the visit, and an interaction term for the treatment-by-visit will be the fixed effects; and the baseline value will be the covariate.

The exploratory efficacy endpoints involving change from baseline will be analyzed at each time point using the same approach (i.e., MMRM) as described for the primary efficacy analysis.

The other efficacy endpoints involving proportions of pruritus NRS, burning sensation NRS, and pain NRS will be analyzed using a Chi-squared test at each visit.

The primary efficacy analysis will be done using the FAS, and the PP analysis set will be used as supportive analysis. No imputation will be performed for the continuous endpoints subjected to an MMRM.

For the analyses of binary data, imputation of the last observation carried forward (LOCF) for any missing value will be performed.

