Abbreviations: anti-HBc, antibody to hepatitis B core antigen; BID, twice daily; ET, early termination; FFA, frontal fibrosing alopecia; FFASS, Frontal Fibrosing Alopecia Severity Score; HBV, hepatitis B virus; HBsAg, hepatitis B surface antigen; HCV, hepatitis C virus; HIV, human immunodeficiency virus; IMP, investigational medicinal product; LPPAI, lichen planopilaris activity index; NRS, Numerical Rating Scale; OLE, open-label extension; TSH, thyroid-stimulating hormone; V, visit.

a For female subjects of childbearing potential, serum pregnancy test at screening and urine pregnancy test at other specified visits.

b Including height and weight. Height will be measured only at screening.

c The lesional target area should be treated with the IMP and should be approximately 3 cm x 6 cm (or equivalent). However, a smaller lesional target area can be selected if tape stripping is performed from the same area where trichoscopy/hair counts is performed or if sample is collected adjacent/close to the lesional target area (refer to Section 8.3.2 for details). If needed, two small lesional target areas (totalling approximately the same size) could be selected to allow for skin samples collection.

d Subjects will complete their NRS at home on a daily basis starting approximately 7 days prior to Day 1 and up to Day 8. On Day 1, the NRS will be completed at the site prior to the first IMP application. After Day 8, the NRS will be completed at the site at the specified visits only.

e Hair line measurements of lateral canthus (right and left) to hairline, lower glabellar crease to hair line, top of frontalis muscle to hair line, and mid brow to hair line (right and left).

f Medical photographs of the target area and the entire scalp (including the frontal hair line and right and left hair line areas).

g The morning application will be on site on visit days. Other IMP applications will be done at home. The first application of the OLE (delgocitinib cream 20 mg/g) is on the morning of Week 12, after all efficacy assessments and skin sample collections are completed. The last application of the OLE is the evening prior to the Week 24 visit. No IMP application will be done on the day of the Week 24 visit.

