### 3 OBJECTIVES AND ENDPOINTS

OBJECTIVES	ENDPOINTS
Primary	
To assess molecular signature changes following topical application of delgocitinib cream 20 mg/g in subjects with FFA	Primary endpoint: 

Change in expression of CXCL9, CXCL10, and IFN-<math>\gamma</math> from baseline to Week 12.

Secondary	Safety endpoint during the vehicle-controlled treatment period: 

Number of TEAEs from baseline to Week 12.

Exploratory	Exploratory safety endpoint: 

Number of TEAEs during the OLE (up to Week 26)

 Exploratory efficacy endpoints during the vehicle-controlled treatment period: 

Change in LPPAI score from baseline to Weeks 4, 8, and 12.

Change in FFASS score from baseline to Weeks 4, 8, and 12.

Change in target area perifollicular erythema score from baseline to Weeks 4, 8, and 12.

Change in target area perifollicular scale score from baseline to Weeks 4, 8, and 12.

Change in pruritus NRS score from baseline to Days 2, 3, 4, 5, 6, 7, 8, and Weeks 4, 8, and 12.

Change in burning sensation NRS score from baseline to Days 2, 3, 4, 5, 6, 7, 8, and Weeks 4, 8, and 12.

Change in pain NRS score from baseline to Days 2, 3, 4, 5, 6, 7, 8, and Weeks 4, 8, and 12.

Proportion of subjects with a 3-point reduction* in pruritus NRS score from baseline to Days 2, 3, 4, 5, 6, 7, 8, and Weeks 4, 8, and 12.

Proportion of subjects with a 4-point reduction* in pruritus NRS score from baseline to Days 2, 3, 4, 5, 6, 7, 8, and Weeks 4, 8, and 12.

OBJECTIVES	ENDPOINTS
	

• Proportion of subjects with a 3-point reduction* in burning sensation NRS score from baseline to Days 2, 3, 4, 5, 6, 7, 8, and Weeks 4, 8, and 12.

• Proportion of subjects with a 4-point reduction* in burning sensation NRS score from baseline to Days 2, 3, 4, 5, 6, 7, 8, and Weeks 4, 8, and 12.

• Proportion of subjects with a 3-point reduction* in pain NRS score from baseline to Days 2, 3, 4, 5, 6, 7, 8, and Weeks 4, 8, and 12.

• Proportion of subjects with a 4-point reduction* in pain NRS score from baseline to Days 2, 3, 4, 5, 6, 7, 8, and Weeks 4, 8, and 12.

• Change in target area hair counts/trichoscopy via fotofinder trichovision from baseline to Week 12.

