## 7.1 Discontinuation

For Cohort 1, subjects who discontinue the trial after the first dose will be asked, if they agree, to come for a last assessment (ET visit). Subjects who are discontinued for safety reasons may be asked to come for additional follow-up visits, at the investigator's discretion, after the ET visit to ensure appropriate medical care and AEs follow-up.

Subjects who discontinue will not be replaced.

Reasons for discontinuation include the following:

- The investigator decides that the subject should be withdrawn. If this decision is made because of an SAE, the IMP is to be discontinued in that subject immediately and appropriate measures are to be taken. The investigator will notify the sponsor immediately.
- If an application site reaction occurs, the investigator should use his or her best medical judgement as to whether to continue subject's treatment.
- The attending physician requests that the subject be withdrawn from the trial.
- The subject, for any reason, requires treatment with another therapeutic agent that has been demonstrated to be effective for treatment of the trial indication. In this case, discontinuation from the trial occurs immediately upon introduction of the new agent.
- The subject is lost to follow-up. In this case, a reasonable attempt to contact the subject and ascertain his or her status must be made, and these attempts must be documented.
- The subject becomes pregnant at any time during the trial.
- Other: the subject may withdraw from the trial for any other reason, including withdrawal of consent.
- The sponsor or regulatory authorities, for any reason, stop the trial. In this case, all subjects will be discontinued from the trial. The investigator will immediately, on discontinuance of the trial by the sponsor, in its entirety or at a clinical trial site, inform both the subjects and the research ethics board of the discontinuance, provide them with the reasons for the discontinuance and advise them in writing of any potential risks to the health of subjects or other persons.

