#### **8.1.4 Pruritus Numerical Rating Scale**

The intensity of pruritus due to FFA will be recorded using a NRS. It will be assessed daily starting approximately 7 days prior to Day 1 and up to Day 8. Thereafter, it will be assessed only at the visits specified in [Table 1](#). This will be evaluated by asking subjects to assign a numerical score representing of the worst intensity over the last 24 hours of their symptoms on a scale from 0 to 10, with 0 indicating no symptoms and 10 indicating the worst imaginable symptoms. The NRS of pruritus is presented in [Appendix C](#).

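### LOCF for the NRS responder endpoints lets a subject who has left the trial count as a responder up to Week 12, and no rule says whether early termination scores are used

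*Combined protocol and SAP*

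**What the plan says.** **Imputation rule.** Section 9.3.3.1 treats the two kinds of NRS endpoint differently. For change scores, "No imputation will be performed for the continuous endpoints subjected to an MMRM". For responder status, "imputation of the last observation carried forward (LOCF) for any missing value will be performed". The rule does not depend on why a value is missing or how old the carried value is.

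**Endpoints and schedule.** Section 3 defines the pruritus responder endpoints as reductions "in pruritus NRS score from baseline to Days 2, 3, 4, 5, 6, 7, 8, and Weeks 4, 8, and 12", and the burning and pain endpoints at the same time points. Table 1, footnote d, sets the collection: "Subjects will complete their NRS at home on a daily basis starting approximately 7 days prior to Day 1 and up to Day 8". It then adds: "After Day 8, the NRS will be completed at the site at the specified visits only". The next scheduled score after Day 8 is therefore Week 4. Each post-baseline score is a single recall, "representing of the worst intensity over the last 24 hours of their symptoms on a scale from 0 to 10" (Section 8.1.4). Baseline is the mean of the daily scores over the 7 days before randomization (Section 9.3.2).

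**Leaving the trial.** Under Section 7.1, when a subject needs another agent shown to be effective for the trial indication, "discontinuation from the trial occurs immediately upon introduction of the new agent". Subjects who discontinue after the first dose are asked to attend an ET visit if they agree. Table 1 schedules all three NRS at that visit. No section says whether an ET score is assigned to a visit or used as the last observation.

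**The concern.** Responder status at Week 12 should describe how the subject is doing on assigned treatment at Week 12. Under the rule as written, someone who has left the trial, including someone who left to start another FFA therapy, keeps whatever status the last recorded score gave. That score is one day's recall set against a 7-day mean baseline, so one good day is enough to create a response that is then held to Week 12.

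The arms are small, and the responder denominators are smaller still if some subjects have baseline scores below 3 or 4. One or two carried responses can therefore change how an endpoint reads. The error could favour either arm, depending on where the departures fall.

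**Working it through.** No figure in the plan depends on this rule, so there is none to reproduce. The check has three parts.

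**1. How far a value can be carried.** Week 12 is taken as Day 12 × 7 + 1 = Day 85. For a subject who leaves after Day 8 and before Week 4 with no ET score used:
- Last score on Day 8: 85 − 8 = 77 days = 11 weeks.
- Last score on Day 2, later diary days also missing: 85 − 2 = 83 days.

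The same value fills Weeks 4, 8 and 12. If an ET score exists and is used, that score is carried instead. The carry is then shorter, but a response recorded at ET is still held to Week 12.

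**2. Effect of one carried response on an arm's rate.** About 30 subjects are randomized 1:1 (Section 6.3), so at most about 15 per arm are evaluable. The baseline thresholds in Section 3 (≥3 or ≥4) may reduce this. The smaller denominators are assumptions. Change in rate = 100 / n:

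| Evaluable per arm | Change per carried response |
|---|---|
| 15 | 6.7 points |
| 10 | 10 points |
| 5 | 20 points |

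**3. Effect on a test result.** Section 9.3.3.1 plans a chi-squared test at each visit, and Section 9.3.1 sets a default two-sided 0.05 level. The counts below are assumed, with 15 per arm, using Pearson's statistic without continuity correction: χ² = N(ad − bc)² / (product of the four margins).

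| Responders, active vs vehicle | χ² | p |
|---|---|---|
| 5 vs 1 (leavers counted as non-responders) | 30 × (5×14 − 10×1)² / (15×15×6×24) = 3.33 | 0.068 |
| 6 vs 1 (one response carried on active) | 30 × (6×14 − 9×1)² / (15×15×7×23) = 4.66 | 0.031 |
| 6 vs 2 (from 6 vs 1, one response carried on vehicle) | 30 × (6×13 − 9×2)² / (15×15×8×22) = 2.73 | 0.099 |

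One subject moves the result across 0.05 in either direction. This is specific to the named test and these counts: Fisher's exact test gives 0.169, 0.080 and 0.215 on the same tables.

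**The case against.** **The ET visit weakens the worst case.** A reader might infer that everyone who leaves before Week 4 has a first-week diary score carried to Week 12. The documents do not support that. Table 1 schedules the NRS at ET, and Section 7 asks for all efforts to complete those examinations. A subject leaving because of poor effect would probably record a non-response there. The long carry needs three things together: exit before Week 4, a response at the last diary entry, and no ET score used. This objection stands, and it limits the first-week case. It does not remove the gap, because attendance is voluntary and the use of ET scores is undefined.

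**Outcome-related dropout is possible but not shown.** Lack of effect is not a listed reason for discontinuation, Section 2.1.1 says there is no standard regimen for FFA, and completers all go on to active drug, which is a reason to stay. This stands as a limit on how often the problem would arise.

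**The contrast with the MMRM is not itself an error.** A reader might infer that LOCF is wrong because the same scores are analysed elsewhere without imputation. That argument proves too much, since non-responder imputation would also differ from the MMRM assumption.

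**The details may be settled elsewhere.** Section 9.3.1 leaves techniques for missing values to a separate SAP, which is not in the text this point rests on. It could refine the rule, but Section 9.3.3.1 already names LOCF for any missing value.

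**Conclusion.** The point holds as a low-cost improvement to exploratory endpoints. Followed as written, Section 9.3.3.1 can count a subject who has left the trial, or left it for another FFA therapy, as a responder up to Week 12, and the role of ET scores is undefined. Each such subject is worth 6.7 points at 15 evaluable per arm and 10 points at 10.

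Compared with counting leavers as non-responders, LOCF can only raise an arm's rate. The treatment difference is overstated if more responses are carried on active, and understated if more are carried on vehicle.

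A reader might infer a quantified loss of power or a definite bias against the drug. The documents support neither. They give no dropout or responder rates, and Section 9.1 sizes the trial on gene expression only. The primary analysis is unaffected, and the NRS change scores are analysed separately without carry-forward. The p-values above show how sensitive the result is to one subject. They do not predict this trial's result.

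**What to change.** In Section 9.3.3.1, and in the separate SAP, replace the LOCF sentence for the 3- and 4-point NRS responder endpoints with a rule that says:

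- Subjects count as non-responders at all scheduled time points after discontinuation or after starting another FFA therapy. No response from an earlier score or from the ET visit is carried past that point.
- For a subject still in the trial, an isolated missing time point counts as non-response in the primary analysis of these endpoints.
- LOCF is kept as a sensitivity analysis, with a statement of whether ET scores enter it.

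The cost is a few lines of text, with no change to data collection or subject management. The rule is slightly conservative for subjects whose scores are missing for unrelated reasons, and it can favour the arm with fewer dropouts. The LOCF sensitivity analysis will show how much that matters.

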#### 9.3.3.2 Open-Label Extension Period

These efficacy outcomes will be measured at scheduled visits after Week 12. The following endpoints will be assessed in the OLE:

- Continuous variables: observed value and change (percent) from baseline in LPPAI, FFASS, target area perifollicular scale score, target area perifollicular erythema score, pruritus NRS, burning sensation NRS, pain NRS, and target area hair counts/trichoscopy via fotofinder trichovision.

The above endpoints will be summarized by visit using descriptive statistics with following considerations:

- Summaries will be provided for 1) treatment group in OLE and for 2) randomized treatment groups in the vehicle-controlled treatment period.
- Change from baseline in continuous variables will be analyzed using change from vehicle-controlled treatment period baseline.

### 9.3.4 Safety Analyses

#### 9.3.4.1 Vehicle-Controlled Treatment Period

##### Cohort 1:

All safety data, including AEs and SAEs will be presented and tabulated according to the Medical Dictionary for Regulatory Activities (MedDRA) classification. Descriptions of AEs will include the start date, the stop date (if it resolved), the severity and seriousness of the AE, the causality of the AE to IMP, and the outcome. The focus in this protocol will be the number of treatment-emergent adverse events (TEAEs).

Adverse events will be considered in vehicle-controlled treatment period or OLE depending on the onset date – if the AE onset date was before Week 12, the AE will be considered as a vehicle-controlled treatment period AE. If the AE had an onset on or after Week 12, the AE will be considered as an OLE AE.

Reported AEs will be summarized by the number of subjects reporting the events, as well as by System Organ Class (SOC), PT, severity, seriousness, and relationship to IMP. For the summary of AEs by severity, each subject will be counted only once within a SOC or a PT by using the AEs with the highest intensity within each category for each analysis. For the summary of AEs by relationship to IMP, each subject will be counted only once within a SOC or a PT by using the AEs with the greatest reported relationship within each category. For the summary of AEs by relationship to IMP and severity, each subject will be counted only once within a SOC or a PT by using (1) the greatest reported relationship followed by (2) the highest reported intensity.

All information pertaining to AEs noted during the trial will be listed by subject, detailing verbatim, SOC, PT, start date, stop date, intensity, outcome, and relationship to IMP. The AE onset will also be shown relative (in number of days) to the day of IMP administration. Serious adverse events will be tabulated by treatment group, relationship to the IMP, and a reference to the occurrence of the SAEs to the relative day of dosing.

AESIs will be listed. No narratives for AESIs will be written in the study report.

Results from laboratory analyses and vital signs will be tabulated by treatment and visit using descriptive statistics. The value at each visit as well as the change from baseline will be presented descriptively.

Clinically significant changes in laboratory analyses and vital signs, and new findings on local tolerability assessments and physical examination will be recorded as AEs.

Concomitant medications will be coded with the world health organization (WHO)-Drug Dictionary and listed by subject. Summary of medication classes will also be tabulated.

No inferential statistics will be done on safety variables.

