# 1 PROTOCOL SUMMARY

## 1.1 Synopsis

Name of Sponsor/Company:	Name of Investigational Product:	Name of Active Ingredient:
LEO Pharma A/S	Delgocitinib cream 20 mg/g	Delgocitinib
Title of Trial:		
A Phase 2a, Randomized, Double-Blind, Vehicle-Controlled, Single Site, Exploratory Trial to Assess the Effect of Delgocitinib Cream 20 mg/g on the Molecular Signature, Safety, and Efficacy in Adults with Frontal Fibrosing Alopecia		
Phase of Development:		
Phase 2a		
Trial Site:		
This trial will be conducted at 1 site located in the United States PPD [REDACTED] Boston, MA).		
Number of Subjects (planned):		

• Cohort 1

- Approximately 30 subjects with frontal fibrosing alopecia (FFA) will be randomized in this cohort.

• Cohort 2

- Approximately 5 healthy postmenopausal female subjects will be included in this cohort.

		
Duration of Trial:		

• Cohort 1

- The maximum trial duration per subject is approximately 30 weeks, including up to 30 days for the screening period, 12 weeks for the vehicle-controlled treatment period, 12 weeks for the open-label extension (OLE), and approximately 2 weeks for the safety follow-up period.

• Cohort 2

- The maximum trial duration per subject is approximately 6 weeks, including up to 30 days for the screening period, 1 day for the skin samples collection, and up to 14 days for the optional follow-up period.

		
Investigational Medicinal Product, Dosage, and Mode of Administration:		
Delgocitinib cream 20 mg/g and matching vehicle (delgocitinib cream vehicle).		

• Cohort 1

- Subjects will be randomized in a 1:1 ratio on Day 1 to apply delgocitinib cream 20 mg/g or vehicle cream twice daily (BID) for 12 weeks during the vehicle-controlled treatment period.

		

Name of Sponsor/Company:	Name of Investigational Product:	Name of Active Ingredient:
LEO Pharma A/S	Delgocitinib cream 20 mg/g	Delgocitinib

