#### **8.5.2 Definition of Treatment-Emergent Adverse Event**

A TEAE is any condition that was not present prior to treatment with the IMP but appeared following treatment, was present at treatment initiation but worsened during treatment, or was present at treatment initiation but resolved and then reappeared while the individual was on treatment (regardless of the intensity of the AE when the treatment was initiated).

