#### 8.5.4.2 Adverse Event Severity

The intensity of an AE is an estimate of the relative severity of the event made by the investigator based on his or her clinical experience and familiarity with the literature. The following definitions are to be used to rate the severity of an AE:

- Mild: The symptom is barely noticeable to the subject and does not influence performance of daily activities. Treatment is not ordinarily indicated.
- Moderate: The symptom is sufficiently severe to make the subject uncomfortable, and performance of daily activities is influenced. Treatment may be necessary.
- Severe: The symptom causes severe discomfort, and daily activities are significantly impaired or prevented. Treatment may be necessary.

If the AE worsens in severity, the new severity, including date of severity change, should be recorded.

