#### **9.3.4.2 Open-Label Extension Period**

Safety analyses will follow general considerations in previous Section [9.3.4.1](#) with the following exceptions:

- Summaries will be provided for 1) treatment group in the OLE and for 2) randomized treatment groups in vehicle-controlled treatment period.
- Change from baseline will be analyzed using change from vehicle-controlled treatment period baseline for subjects who received delgocitinib during the vehicle-controlled treatment period, and change from OLE baseline for subjects who received placebo during the vehicle-controlled treatment period.

Only descriptive statistics will be presented.

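### Adverse events are assigned to a period by onset date alone, so an event that starts on vehicle and worsens after the Week 12 switch to delgocitinib is by default not counted in the open-label extension

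*Combined protocol and SAP*

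**What the plan says.** Section 9.3.4.1 makes onset the only criterion: "Adverse events will be considered in vehicle-controlled treatment period or OLE depending on the onset date". The two branches are "if the AE onset date was before Week 12, the AE will be considered as a vehicle-controlled treatment period AE" and "If the AE had an onset on or after Week 12, the AE will be considered as an OLE AE".

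For the OLE, Section 9.3.4.2 begins "Safety analyses will follow general considerations in previous Section" 9.3.4.1 and then lists two exceptions. One concerns the groups to be summarised, the other the reference point for change from baseline. Neither concerns the period to which an AE belongs.

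Three other provisions bear on an event that changes over time:

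- Section 8.5.2 counts as treatment-emergent a condition that "was present at treatment initiation but worsened during treatment".
- Section 8.5.4.2 tells sites: "If the AE worsens in severity, the new severity, including date of severity change, should be recorded".
- The severity summary in Section 9.3.4.1 says "each subject will be counted only once within a SOC or a PT by using the AEs with the highest intensity within each category". It sets no cut-off at the end of the period.

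Section 3 makes the TEAE count to Week 12 the secondary endpoint and the OLE count, up to Week 26, an exploratory safety endpoint.

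**The concern.** Subjects who complete the controlled period on vehicle have their first delgocitinib exposure at Week 12. For them, an event already present that gets worse on active cream is first-exposure safety information. An onset-only rule does not see it, because the onset date precedes the switch.

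The plan treats these subjects as new starters elsewhere. Section 9.3.4.2 resets change from baseline to the OLE baseline for those who came from vehicle, and the version history records an FDA recommendation that all who initiate delgocitinib be monitored similarly, whichever period they start in. AE classification has no matching provision. A condition present at Day 1 that worsens on delgocitinib is a TEAE of the controlled period; one present at the switch that worsens on delgocitinib is not an OLE TEAE. The gap affects any event ongoing at the switch, wherever on the Week 12 visit day the cut is placed.

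**Working it through.** Safety is descriptive, so there is no planned power, alpha or effect size to reproduce. The check applies the rule to a test case and then shows the possible scale.

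**Inputs**

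- About 30 subjects randomised 1:1 (Section 6.3): 30/2 = 15 per arm, before dropout.
- First OLE application on the morning of the Week 12 visit (Table 1, footnote g). With Day 1 as the first dose, Week 12 is taken as Day 1 + 12 × 7 = Day 85.
- The period rule, the severity-recording rule and the severity-table rule as set out above.

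**Step 1: period assignment.** Take a vehicle subject with a mild AE starting on Day 70 that becomes severe on Day 100.

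| How the worsening is recorded | Onset used | Comparison | Period | Added to OLE count |
|---|---|---|---|---|
| Same AE, dated severity change | Day 70 | 70 < 85 | Vehicle-controlled | 0 |
| New AE record | Day 100 | 100 ≥ 85 | OLE | 1 |

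Section 8.5.4.2 reads most naturally as the first row: the new severity and its date are attributes of the AE that worsened. Section 8.5.4.3 ties the stop date of a recovered event to the event having stopped, and a worsened event has not. The protocol does not expressly exclude the second row, so classification turns on a data-entry convention that it does not state.

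**Step 2: grade shown.** Under the first row, the severity table may take the Day 100 grade (severe) for a controlled-period AE, since no cut-off is given. With a cut-off at the switch it would take mild. The greatest-relationship rule in Section 9.3.4.1 has the same gap, and no cut-off is stated for seriousness either.

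**Step 3: both arms.** Subjects randomised to delgocitinib also continue for 12 weeks in the OLE. If they have an AE that started before Week 12 and worsened later, the same reading brings its later grade into the delgocitinib column. The controlled-period tables can therefore shift in either column.

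**Step 4: scale.** One subject is 1/15 = 6.7 percentage points of an arm. The documents give no AE rates, so p below, the chance that a given switcher has a carried-over AE that worsens, is an assumption. Expected number affected = n × p; chance of at least one = 1 − (1 − p)^n.

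| p (assumed) | Expected, n = 15 | At least one, n = 15 | At least one, n = 12 |
|---|---|---|---|
| 2% | 0.3 | 26% | 22% |
| 5% | 0.75 | 54% | 46% |
| 10% | 1.5 | 79% | 72% |
| 20% | 3.0 | 96% | 93% |

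The n = 12 column allows for three vehicle subjects not entering the OLE, also an assumption.

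**The case against.** The strongest reply is that the gap is narrow and that several larger claims cannot be built on it. Most of that stands.

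- A reader might infer that the event will appear under vehicle at its worst grade. The documents do not establish this. It needs the worsening to stay in one record and the highest-intensity rule to reach past the end of the period. The first is likely, but neither is stated.
- A reader might infer that delgocitinib is made to look safer throughout. Later grades could enter the delgocitinib column too, so the net direction in the controlled-period tables is indeterminate. The secondary count is untouched: an event that began on vehicle belongs there whatever follows.
- A reader might see a contradiction with Section 8.5.2. There is none. That definition runs from the start of the investigational product, which the Synopsis defines to include vehicle. For vehicle subjects that is Day 1, and nothing restarts it at the switch.
- Recurrence after resolution needs no new rule if it is entered as a new event, because its own onset date already places it in the OLE.
- The stakes are limited. There is no inference on safety, the OLE endpoint is exploratory, AEs are listed by subject, serious events carry a narrative, and worsening of the alopecia itself is not recorded as an AE (Section 8.5.12).
- Section 9.3.1 leaves safety variable definitions to a separate SAP, which is not in the material reviewed and may settle the matter.

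Two things remain. The protocol has already fixed onset as the sole criterion, so this is a stated rule with a consequence and not only an open detail. And the by-subject listing does not fully repair it: its specified items include start date, stop date and intensity but not the date of severity change, so a reader could not tell that worsening followed the switch.

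**Conclusion.** The concern holds in a limited form. Followed as written, the onset-only rule leaves post-switch worsening out of the OLE TEAE count, including worsening on first delgocitinib exposure in former vehicle subjects. Compared with a rule that counts worsening, it can only lower that count. This rests on the worsening staying in the same AE record, the more natural reading of Section 8.5.4.2. On that same reading, the controlled-period severity, relationship and seriousness tables may carry values from after the period, in either arm and with no determinable direction.

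The size is unknown: about 6.7 points of a 15-subject arm for each affected subject, with no AE rates in the documents to say how many there would be. This does not threaten the secondary endpoint and is not a demonstrated bias in favour of delgocitinib. It is a cheap improvement worth making before database lock.

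**What to change.** In Sections 9.3.4.1 and 9.3.4.2:

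- **(a) Count.** Treat an AE that is ongoing at the first OLE application and later increases in severity or becomes serious as an OLE TEAE, dated at the worsening. Apply this to both randomised groups, so that they are counted under one rule, and show the result by randomised group, so that first delgocitinib exposure in former vehicle subjects is visible.
- **(b) Grade.** For both arms, base severity, relationship and seriousness in each period's tables only on values reached within that period.
- **(c) List.** Add the date of severity change to the by-subject AE listing.

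State also in Section 8.5.4.2 whether a worsening stays in the same AE record, so that sites do not decide the classification by how they enter it.

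The cost is wording and one derivation. The date of severity change is already to be recorded under Section 8.5.4.2. The protocol does not say that dates of change in relationship or seriousness are recorded on the AE form, so the sponsor should check that the case report form supports (a) and (b) for those items. The downside is that a worsened event appears in both period tables; a footnote should say so, and that the two period counts must not be added.
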